3.8. Subgroups

The primary endpoint overall survival will be analyzed in an exploratory way in subgroups defined by strata and other factors assessed at the screening phase:

- Tumor Subtype: Luminal A, Luminal B, Her2 and Basal
- Grading: G1/G2/GX and G3
- HER 2: FISH amplif./IHC++, Her2 Negative
- Hormone receptor status: any positive, 0/0
- First Line Therapy: Chemotherapy vs Others
- Location of metastases: bone only, visceral +/- bone

Subtypes were defined as follows:

Luminal A = HR+, Her2-, G1/2/X

Luminal B: HR+, Her2-, G3

Her2: Her2+

Basal: HR-, Her2-

Subgroups other than stratification variables will be re-examined for appropriateness.

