2.3. Randomization and stratification criteria

The randomization system used is the software ‘Randomizer’ which was developed and is maintained by the Institute of Medical Statistics and Informatics at the Medical University of Vienna. In accordance to the inclusion and exclusion criteria, patients are randomized to one of the following arms:

A: Surgical Therapy
 B: Surgery on Demand

Patients were stratified with respect to following stratification factors:

- Center
- Grading
 - G1/G2 **versus** G3/GX
- Receptor status
 - 0/0 **versus** any positive
- Her2neu status
 - FISH amplified/IHC+++ **versus** negative
- Location of metastases
 - visceral ± **versus** bone only
- Planned first line therapy
 - Anthracycline-based ± any other except taxane **versus** taxane based ± any other **versus** any other therapy

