3.1.3. Stratification errors

Stratification errors are defined as different values in the stratification factors compared between the randomization system and actual patient values from the electronic case report forms (eCRF).

Stratified analyses that are intended to evaluate the treatment effect will be based on the randomized stratum. If stratification error for a factor includes more than 10% of value, actual value instead of randomized stratum will be used in analysis.

Covariate analyses will be based on subject's actual values.

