3.5.3. Efficacy analysis for primary endpoint

For the primary endpoint, a *2-sided log-rank* test (unstratified) will be used to test for differences between local therapy versus no local therapy at an overall alpha level of 0.05.

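### SAP 3.8 labels the HER2-positive subgroup with IHC++ where the randomisation stratum uses IHC+++, and the plan neither explains the difference nor states a HER2 cut-off for the tumour subtypes

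*SAP*

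**What the plan says.** The HER2 stratification factor in SAP 2.3 is "FISH amplified/IHC+++ versus negative". The protocol's two stratification lists, in the synopsis and in the main text, give the same two levels. The narrative design descriptions (protocol synopsis and SAP section 2) name no score, but they place tumours of undeterminable HER2 status with the negatives.

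SAP 3.8 says that overall survival "will be analyzed in an exploratory way in subgroups defined by strata and other factors assessed at the screening phase", and gives the HER2 subgroup as "HER 2: FISH amplif./IHC++, Her2 Negative". The same section builds four tumour subtypes from HER2 status, for example "Luminal A = HR+, Her2-, G1/2/X". The subtype rules use Her2+ and Her2- without an IHC or FISH criterion. The section closes with "Subgroups other than stratification variables will be re-examined for appropriateness".

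SAP section 5 records one change from the protocol: centre replaced geographic region in the randomisation. It records no change to the HER2 cut-off.

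**The concern.** A cut-off in an analysis section is an instruction to the programmer. Here the instruction differs by one IHC grade from the definition under which patients were randomised, and the plan gives no reason. Followed to the letter, it would put tumours that the stratum treats as HER2-negative into the HER2-positive row of the forest plot (SAP 4.4, item 15). A reader would take that row to describe the randomisation stratum.

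The subtype rows raise a related question. Their definitions depend on HER2 status, and the only HER2 cut-off in SAP 3.8 is the IHC++ line. If that line governs the subtypes, the same tumours would leave Luminal A, Luminal B or Basal and enter Her2. What is at stake is the reading of exploratory results by HER2 status and subtype.

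**Working it through.** The plan states no figure to reproduce here, so the check is a comparison of the rules. Each combination of IHC score and FISH result is classified under the stratum rule and under two literal readings of the subgroup label.

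- Stratum (SAP 2.3 and protocol): positive if FISH amplified or IHC 3+.
- Reading 1 of SAP 3.8: positive if FISH amplified or IHC 2+ and above.
- Reading 2 of SAP 3.8: positive if FISH amplified or IHC exactly 2+.

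| IHC | FISH | Stratum | Reading 1 | Reading 2 |
|---|---|---|---|---|
| any | amplified | positive | positive | positive |
| 0 or 1+ | unamplified or not done | negative | negative | negative |
| 2+ | unamplified or not done | negative | **positive** | **positive** |
| 3+ | unamplified or not done | positive | positive | **negative** |

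The results are:

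1. With four IHC scores and three FISH states there are 4 × 3 = 12 combinations. Reading 1 disagrees with the stratum in 2 of them: IHC 2+ with FISH unamplified, and IHC 2+ with FISH not done.
2. Reading 2 disagrees in those 2 and in 2 more (IHC 3+ with FISH unamplified or not done), so 4 of 12. It would call IHC 3+ tumours without amplification negative, which is implausible and points towards a typing error.
3. If the label is a typing error for IHC+++, 0 of 12 combinations differ and no patient moves.
4. If the subtypes use the SAP 3.8 cut-off under reading 1, the reclassified tumours enter Her2. They come from Luminal A (hormone-receptor-positive, G1/2/X), Luminal B (hormone-receptor-positive, G3) or Basal (hormone-receptor-negative). If the subtypes use the stratum's cut-off, none of them moves.

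These are counts of combinations, not of patients. Turning them into patients needs the share of tumours that are IHC 2+ without amplification. Neither document gives it.

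Next, which analyses use the HER2 grouping:

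- Primary test (SAP 3.5.3): the two-sided log-rank "test (unstratified) will be used to test for differences between local therapy versus no local therapy at an overall alpha level of 0.05". HER2 does not enter it.
- Stratified log-rank (SAP 3.5.4): under SAP 3.1.3, "Stratified analyses that are intended to evaluate the treatment effect will be based on the randomized stratum", with a switch to actual values for a factor whose error rate exceeds 10%. The SAP 3.8 label does not define the randomised stratum.
- Forest plot of overall survival by subgroup (SAP 3.8; item 15): directly affected.
- Cox models: HER2 status and tumour subtype are candidate covariates in SAP 3.9, with HER2 taken from the eCRF. No cut-off is stated there, so an effect would depend on whether the SAP 3.8 derivation is reused.

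**The case against.** The strongest reply is that this is a slip of the keyboard. SAP 3.8 says its subgroups come from the strata, HER2 is a stratum, and section 5 declares no change. Taken exactly, IHC++ would leave IHC 3+ without a home. On that view the label means IHC+++ and nothing moves. This is a likely explanation, and it rules out presenting misclassification as a fact.

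It does not make the correction unnecessary. The same list departs from the strata in other places. GX is grouped with G3 in SAP 2.3 but with G1/G2 in SAP 3.8, and first-line therapy falls from three levels to two. A programmer therefore cannot assume that every line of SAP 3.8 means the stratum. The closing clause on re-examination does not help with the HER2 subgroup either, because it covers only subgroups that are not stratification variables. It does cover tumour subtype.

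Three stronger conclusions are tempting, and the documents do not support them:

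- **IHC 2+ unamplified tumours are analysed in the wrong HER2 and subtype groups.** The HER2 part depends on the label being programmed literally. The subtype part also depends on Her2+ taking its cut-off from that label, which is a natural inference within SAP 3.8 but is nowhere stated.
- **The forest plot will contradict the stratified test and the HER2 covariate.** The stratified test gives no HER2-specific estimate that could be contradicted, and the covariate's cut-off is not given.
- **A particular number of patients is affected.** Any count would rest on an assumed IHC 2+ share and an assumed HER2-positive share, and an honest range would have to start at zero.

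**Conclusion.** The inconsistency is real, unexplained and minor. SAP 3.8 gives a HER2 cut-off that conflicts with the stratification definition in SAP 2.3 and the protocol. Whether any patient is regrouped depends on two things that the documents leave open: whether the label is a typing error, and whether the subtypes share its cut-off. The effect runs from none, if a plus sign was dropped, to every tumour that is IHC 2+ without demonstrated amplification. Under the exact reading, IHC 3+ tumours without demonstrated amplification would be regrouped as well.

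The consequence is confined mainly to the exploratory overall survival subgroups. It would reach the Cox models only if the same derivation were reused there. The primary comparison, its type I error and its power are untouched.

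**What to change.** In SAP 3.8, define the HER2 subgroup as in SAP 2.3, "FISH amplified/IHC+++ versus negative". If a different cut-off is intended, state it in full, including where IHC 3+ and tumours without a FISH result belong, and record it with a reason in section 5.

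In the subtype definitions, add that Her2+ and Her2- are taken from that same variable.

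The cost is a correction of one line and one added sentence, made before the subgroup analyses are programmed. No data collection, sample size or primary analysis changes.

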3.9. Covariates

To adjust for the possible effect of demographic or prognostic factors multivariate analyses will be performed. To avoid multi-collinearity between the covariates, prior correlation analyses will be performed. Depending on the statistical results and the clinical relevance, highly correlated covariates may be excluded from multivariate analyses. Binary dependent variables will be analyzed using logistic regression models. Metric dependent variables will be analyzed using general linear models or a non-parametric equivalent if appropriate. Forest plots will be given where appropriate.

The following variables are candidates for covariates which will be used for analyses to explore the relationship to the primary and secondary endpoints:

- Age group*
- T-stage
- N-stage
- Histologic grade
- Hormone Receptor status*
- HER2 status*
- Tumor Subtype

- Endocrine therapy
- Chemotherapy
- Immunotherapy
- Location of metastases

*Based on patient's actual value (eCRF)

3.10. Software

All analyses will be done using SAS version 9.3 or higher.

4. List of Planned Tables, Figures and Listings

4.1. Baseline demographic and disease characteristics

1. Demographic data of patients, stratification factors and disease characteristic variables in total and by treatment arm
2. Surgery and tumor classification after surgery
3. Patient status summarized in total and by treatment arm

4.2. Primary endpoint

4. Deaths in total and by treatment arm (randomized patients)
5. Result of Log-rank test for OS with treatment arm as covariate without stratification
6. Result of Log-rank test for OS with treatment arm as covariate with randomization stratification
7. Result of multivariable Cox proportional hazard model for OS with treatment arm, and stratification factors* as additional covariates
8. Result of multivariable Cox proportional hazard model for OS with treatment arm and prognostic factors as additional covariates

*actual values (eCRF)

4.3. Secondary endpoints

9. Result of Log-rank test for Time to distant progression with treatment arm as covariate
10. Result of Log-rank test for Time to local progression with treatment arm as covariate
11. Result of Log-rank test for TTPd with treatment arm as covariate with randomization stratification
12. Result of Log-rank test for TTPI with treatment arm as covariate with randomization stratification

13. Result of multivariable Cox proportional hazard model for TTPd with treatment arm, as well as stratification factors and prognostic factors as additional covariates
14. Result of multivariable Cox proportional hazard model for TTPI with treatment arm, as well as stratification factors and prognostic factors as additional covariates

4.4. Exploratory endpoints

15. Forest Plot of Hazard Ratios by Patient Subgroups

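### The SAP plots survival hazard ratios for 14 overlapping subgroup rows but plans no treatment-by-factor test, so chance differences between rows may be read as different effects

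*SAP*

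**What the plan says.** SAP 3.8 states: "The primary endpoint overall survival will be analyzed in an exploratory way in subgroups defined by strata" and by other screening factors. It then lists six factors:

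- "Tumor Subtype: Luminal A, Luminal B, Her2 and Basal" (4 levels)
- "Grading: G1/G2/GX and G3" (2)
- "HER 2: FISH amplif./IHC++, Her2 Negative" (2)
- "Hormone receptor status: any positive, 0/0" (2)
- "First Line Therapy: Chemotherapy vs Others" (2)
- "Location of metastases: bone only, visceral +/- bone" (2)

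The same section builds tumour subtype from receptor status, HER2 and grade, and its Her2 subtype consists of the HER2-positive patients. Subgroups that are not stratification variables are to be reconsidered for suitability.

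The only planned output is item 15 in SAP 4.4, "Forest Plot of Hazard Ratios by Patient Subgroups". The Cox models in SAP 3.5.4, 4.2 and 4.3 and in the protocol's statistical section enter arm and other factors side by side as covariates. SAP 3.9 describes covariate adjustment. None of these places names an interaction term or a heterogeneity test, and 3.8 has no rule for reading the rows other than its exploratory label.

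**The concern.** A subgroup forest plot invites one question: does the effect of local therapy differ between, say, bone-only and visceral disease? Separate hazard ratios do not answer it. A row whose interval excludes 1 beside a row whose interval does not is not evidence that the two effects differ, since the smaller row may simply hold fewer deaths. The covariate models do not fill the gap either, because each assumes one common treatment effect across the levels of every factor.

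The trial is sized for a single overall comparison, so each row is estimated imprecisely and rows will scatter even when the true effect is the same for everyone. What is at stake is the interpretation of one exploratory figure, in a setting where a subgroup-specific message about surgery could be taken up.

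**Working it through.** **Inputs.** Target hazard ratio 0.666, two-sided 5% level and 80% power (SAP 2.4; protocol, sample size considerations); 192 deaths (protocol, same section); 1:1 allocation; factor levels from SAP 3.8. The documents give no subgroup prevalences, so the splits of deaths below are assumptions.

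**The plan's own figure.** Schoenfeld's formula gives 4 × (1.960 + 0.842)² / (ln 0.666)² = 4 × 7.85 / 0.1652, about 190 and 191 with the tool's rounding. Freedman's gives 196. With 192 deaths, power is 80.4%. The protocol's 192 is reproduced.

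**Rows.** 4 + 2 + 2 + 2 + 2 + 2 = 14. The Her2 subtype and the HER2-positive row are the same patients if one definition of positivity serves both, which leaves 13 distinct rows.

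**One two-level factor, same true hazard ratio of 0.666 in both rows.** For a row with d deaths, the standard error of the log hazard ratio is √(4/d), and the chance that its 95% interval excludes 1 is Φ(0.4065 × √d / 2 − 1.96). At d = 96 this is Φ(1.991 − 1.96) = 51%. With row chances a and b, the chance that exactly one interval excludes 1 is a(1 − b) + b(1 − a). The standard error of the difference between the two log hazard ratios is SE = √(4/d1 + 4/d2), so the ratio of hazard ratios reaches exp(1.96 × SE) at the 95% limit by chance alone.

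| Split of 192 deaths | Row chances | Exactly one excludes 1 | SE | Chance ratio, 95% limit |
|---|---|---|---|---|
| 50:50 | 51%, 51% | 50% | 0.289 | 1.76 |
| 30:70 | 34%, 65% | 55% | 0.315 | 1.85 |
| 20:80 | 24%, 71% | 61% | 0.361 | 2.03 |

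**All rows together.** This was simulated with 192 deaths and the six factors overlapping as SAP 3.8 defines them, under three assumed sets of prevalences for receptor-positive, HER2-positive, G3, chemotherapy and visceral disease: 70/25/40/70/65%, 80/20/30/50/80%, and 50% throughout.

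- Hazard ratio 0.666 in everyone: the plot mixes rows that exclude 1 with rows that do not in 92 to 93% of trials. The median ratio of largest to smallest row hazard ratio is about 1.9 to 2.05.
- No effect anywhere: at least one row excludes 1 in 33 to 35% of trials.

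Simulating the trial separately gave about 94% (mixed rows within at least one factor) and 34 to 36%. The combined ranges are 92 to 94% and 33 to 36%.

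**What an interaction test could show.** There would be six tests, five with 1 df and one (subtype) with 3 df. With no heterogeneity, the chance of at least one p < 0.05 is 1 − 0.95⁶ = 26.5% if the tests are independent, and about 24% in simulation with overlapping factors. For a two-level factor, 80% power needs a ratio of hazard ratios of exp(2.80 × SE): 2.25 (50:50), 2.42 (30:70) or 2.75 (20:80). Power for a ratio of 1.5 is 29%, 25% and 20%.

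**The case against.** The strongest reply is that the plan claims nothing here. Both SAP sections label the analysis exploratory, no subgroup conclusion is planned, and the SAP specifies no test or p-value for individual rows. The percentages above therefore describe how a plot might be misread, not an error rate of a planned procedure. That stands, and it limits the point to a risk of misreading. The label does not, however, supply the comparison that the plot invites.

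The figures of 92 to 94% sound alarming partly because they cover all six factors at once and partly because small rows miss significance even when estimates agree. That also stands; the per-factor figure of 50 to 61% is the fairer measure.

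A reader might infer that there are 14 independent looks. The documents do not support that: the rows come from six overlapping factors, subtype is built from three of the others, and one row is a repeat.

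Finally, the remedy is modest. Six nominal tests carry their own 24 to 26.5% chance of a false signal and have little power for moderate differences. Removing row p-values still leaves intervals that do or do not cross 1. This is a reason to state the limits and the reading rule with the tests, not to omit them.

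**Conclusion.** The point holds as a cheap improvement to an exploratory output. As written, the plan can display subgroup hazard ratios but cannot say whether they differ. If the effect is uniform at 0.666 with 192 deaths, a two-level factor has about an even chance or somewhat more (50 to 61%) of showing one row that excludes 1 and one that does not, and hazard ratios apart by a factor of 1.76 to 2.03 remain compatible with chance. These figures rest on the assumed splits of deaths and on the plot carrying 95% intervals; the all-row figures rest also on the assumed prevalences.

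A reader might infer that the plot will mislead, or that it nearly always suggests effects that do not exist. The documents do not support either: they announce no subgroup claim, and with no effect anywhere about one trial in three, not nearly all, shows a row that excludes 1. Nor does the gap touch the primary log-rank test, its alpha level or the sample size.

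**What to change.** In SAP 3.8 and item 15:

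1. For each factor, fit one Cox model with arm, factor and arm-by-factor: 1 df for the five two-level factors, 3 df for tumour subtype.
2. Beside the forest plot, print the interaction p-value and the ratio of hazard ratios with its 95% confidence interval. For subtype, give the ratios against a named reference level together with the 3-df p-value.
3. Give no p-values for single rows.
4. State that subgroup differences are discussed only on the interaction result.
5. State that the six tests are exploratory and unadjusted, with about a 24 to 26% chance of at least one nominal p < 0.05 when there is no heterogeneity, and that power is low: 80% only for a ratio of hazard ratios of about 2.25 to 2.75.
6. Note that the Her2 subtype row and the HER2-positive row show the same patients.

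The cost is six model statements and a short paragraph. No new data are needed. The main drawback is low power: a non-significant interaction must not be presented as proof that the effect is uniform.

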4.5. Safety evaluation

16. Side Effects by SOC in total and by treatment arm

4.6. Other Tables

17. Summary of important protocol deviations in total and by treatment arm
18. Patient status in total and by treatment arm
19. Patient exposure to local systematic therapies
20. Laboratory Values: CEA and CA 15-3 summary per visit
21. List of randomization stratification errors

5. Changes of analysis compared to study protocol

Patients were stratified with in Randomiser respect to center (option “Consider center as a factor”) instead of “Geographic region” as stated in protocol. All stratified tests will be performed without “Geographic region” as the stratification factors .
